## 3.5 STRATIFICATION, RANDOMIZATION, AND BLINDING/MASKING

Participants who sign the informed consent form and meet the eligibility criteria will be randomly assigned 2:1 in favor of treatment with AMG 714 versus treatment with placebo. Random assignment will be stratified by active versus stable vitiligo, as defined in Section 3.4.2.

Randomization will be accomplished through a password-protected, web-based, randomization system.

Randomization will occur at least one day prior to Visit 0.

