## 13.4.4 Analyses of Secondary Endpoints

All secondary inferential analyses are considered supportive; p-values for test of differences among groups will be presented without adjustment for multiple comparisons. The mITT population will be used for all secondary analyses. For secondary response indices (e.g. F-VASI25 at Week 12, F-VASI25 at Week 36, F-VASI25 at Week 48, T-VASI25 at Week 12, etc.), participants for whom endpoint data is unavailable will be deemed response failures. Otherwise, data will not be imputed for analyses of secondary endpoints.

The null hypothesis proposes that there are no differences in the secondary endpoints (measured either as means or proportions) between study groups. The alternative hypothesis proposes that there are differences between groups.

The following analyses are planned to evaluate the impact of treatment over the course of the study:

- 1. For secondary dichotomous response variables including F-VASI25, F-VASI35, F-VASI35, F-VASI50, F-VASI75, F-VASI90, T-VASI25, T-VASI35, T-VASI50, T-VASI75, and T-VASI90 at each indicated secondary analysis time point, analyses will be analogous to those described for the primary endpoint.
- 2. Estimated response rates for each dichotomous F-VASI and T-VASI responder variable (i.e. 25%, 35%, 50%, 75%, 90%) at each indicated analysis time point will be presented for subgroups defined by treatment and active/stable vitiligo status.
- 3. For the change (and % change) in F-VASI, change (and % change) in T-VASI, change in VES, and change in VitiQoL at each indicated secondary analysis time point, the treatment group distributions will be compared using Mann-Whitney tests (2-sided).
- 4. For the ordinal VNS endpoint at each secondary analysis time point,
  - a. Treatment groups will be compared at each indicated secondary analysis time point using an extension of the Fisher's Exact test.
  - b. Shifts in distributions from baseline to each time point will be evaluated for each treatment arm using Bowker's exact test of symmetry.

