5. To evaluate treatment group differences longitudinally, separate general mixed linear models will be fit to the F-VASI, T-VASI, VES, and VitiQoL, over all time points from day 0 through Week 24 with fixed effects for time point (fit as categorical), treatment group and the time\*treatment interaction. A 1-banded unstructured within-subject covariance matrix will be assumed and fit separately for each treatment arm. Appropriate contrasts will evaluate trends over time and changes from baseline.

After Week 24, participants who do not achieve a T-VASI25 response will receive nbUVB phototherapy. For T-VASI25 responders (who will not receive nbUVB phototherapy), the post-Week 24 analyses will evaluate durability of response. In contrast, for T-VASI25 non-responders, the aim will be to evaluate improvement following the addition of nbUVB phototherapy. The following analyses are planned:

- 1. Durability of response: For the subset of participants who achieve a T-VASI25 response at Week 24 (and receive no nbUVB phototherapy), the null hypothesis of no change from Week 24 to Week 48 will be evaluated by treatment arm against the 1-sided alternative of worsening from Week 24 to Week 48.
  - a. For each treatment arm, descriptive statistics and p-values derived from Wilcoxon tests will be presented for change (and % change) in F-VASI, change (and % change) in T-VASI, change in VES, and change in VitiQoL from Week 24 to Week 48.
  - b. For the VNS ordinal endpoint, shifts in distributions from Week 24 to Week 48 will be evaluated for each treatment arm using Bowker's exact test of symmetry.
- 2. Improvement after nbUVB phototherapy: For the subset of participants who do not achieve a T-VASI25 response at Week 24 and receive nbUVB phototherapy, analyses will assess improvement in repigmentation and other key scales in the AMG 714 and placebo arms following nbUVB phototherapy.
  - a. For each treatment arm, descriptive statistics and p-values derived from Wilcoxon tests will be presented for change (and % change) in F-VASI, change (and % change) in T-VASI, change in VES, and change in VitiQoL from baseline to Week 48.
  - b. For dichotomous response indices defined by % improvement from baseline to Week 48 (i.e. F-VASI25, F-VASI35, F-VASI50, F-VASI75, F-VASI90, T-VASI25, T-VASI35, T-VASI50, T-VASI75, and T-VASI90), estimated response rates will be presented for subgroups defined by treatment.
  - c. For the VNS ordinal endpoint at Week 48,

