#### 13.7 SAMPLE SIZE CONSIDERATIONS

The underlying F-VASI35 response rate at Week 24 was assumed to be 5% for the placebo arm based on clinical trial results with ruxolitinib cream for vitiligo. For the AMG 714 arm, the minimal clinically meaningful response rate was assumed to be 45%. Under this scenario, a study of 57 individuals randomized 2:1 to AMG 714 and placebo, respectively, will provide 88% power using a 2-sided Fisher's Exact test at  $\alpha$ =0.05. If the placebo response rate is actually 7.5% (i.e. 50% higher than expected), power will still 81%. For the secondary PP analysis, if sample size drops to 48 (16% loss), then power is still 80%.

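### The Mann-Whitney tests of change in F-VASI, T-VASI, VES and VitiQoL adjust for neither the baseline score nor the randomisation stratum, which can cost some power in a supportive analysis

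*Combined protocol and SAP*

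**What the plan says.** Section 3.5: "Random assignment will be stratified by active versus stable vitiligo, as defined in Section 3.4.2".

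Section 13.4.4, item 3, covers change and percent change in F-VASI and T-VASI, and also "change in VES, and change in VitiQoL at each indicated secondary analysis time point". For all of these, "the treatment group distributions will be compared using Mann-Whitney tests (2-sided"). No covariate or stratification factor is named. The time points are Weeks 12, 24, 36 and 48 (Section 3.3.1).

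Section 13.4.4, item 5, adds mixed models for the same four scales "over all time points from day 0 through Week 24 with fixed effects for time point", treatment and their interaction. The stratum is not among the effects.

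The stratum appears in two other places: a Cochran-Mantel-Haenszel sensitivity analysis of the primary endpoint (Section 13.4.3), and response rates described by treatment and activity status (Section 13.4.4, item 2). Section 13.4.4 calls all secondary inference supportive, without multiplicity adjustment.

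**The concern.** Two pieces of information known before treatment are left out of the between-arm tests on the continuous scales. Patients with a high baseline score have more room to change, so baseline can explain part of the variation in change. Active disease is defined in Section 3.4.2 by new or expanding lesions, so activity may well predict change in extent. The plan controls for activity in a sensitivity analysis of the binary endpoint but in no inferential analysis of the continuous ones.

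At stake is precision. With 57 participants, the continuous scales help to judge whether a proof-of-concept result deserves follow-up. If activity is prognostic, stratified randomisation removes its contribution to chance differences between the arms, but the unstratified test still counts it as noise, so its p-values run somewhat high.

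**Working it through.** **The plan's own power figures.** Section 13.7 states that "a study of 57 individuals randomized 2:1 to AMG 714 and placebo, respectively, will provide 88% power using a 2-sided Fisher's Exact test", at 45% against 5%. The arcsine approximation to Fisher's test gives this:

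power = Φ{2√[n₁n₂/(n₁+n₂)] × [asin√(p₁ − 1/2n₁) − asin√(p₂ + 1/2n₂)] − 1.96}

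With 38 and 19: 2√(722/57) = 7.118; asin√0.4368 − asin√0.0763 = 0.442; 7.118 × 0.442 − 1.96 = 1.19; Φ = 88%. The same formula gives 81% at a 7.5% placebo rate and 80% at 32:16, so all three stated figures reproduce. Exact enumeration gives 92.7%, 85.8% and 85.7%, so they err on the safe side. They concern the binary primary endpoint. No power is stated for the Mann-Whitney tests.

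**Assumptions, because the documents give none of these.** Baseline to follow-up correlation r of 0.5 to 0.95; equal SDs at baseline and follow-up; strata of 30 and 27, each split 2:1; stratum effect of 0 to 0.6 within-stratum SDs of *change*; no missing data. The treatment effect is set so that an unadjusted z-test of change has 80% power: (1.960 + 0.842) × √(1/38 + 1/19) = 2.802 × 0.281 = 0.787 SD of change.

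**Baseline covariate, analytic.** Var(change) = 2σ²(1 − r). ANCOVA residual variance = σ²(1 − r²). The ratio is (1 + r)/2.

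- r = 0.5: ratio 0.75, power Φ(2.802/√0.75 − 1.96) = 90%
- r = 0.7: ratio 0.85, power 86%
- r = 0.9: ratio 0.95, power 82%

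Mann-Whitney on normal data has about 78% throughout: Φ(2.802 × √0.955 − 1.96), where 0.955 is its efficiency relative to the t-test.

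**Stratum and conservatism, analytic.** A stratum effect of e SDs inflates the variance that the unstratified test assumes by about 1 + e²/4. At e = 0.6 this is 1.09, so the true size is about 2[1 − Φ(1.96 × √1.09)] = 4.1%.

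**Simulation, normal data, 3,000 runs per scenario.** Rank ANCOVA regresses the rank of change on treatment, rank of baseline and stratum.

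| r | Stratum effect (SD of change) | Mann-Whitney | Rank ANCOVA |
|---|---|---|---|
| 0.5 | 0 | 75% | 84% |
| 0.7 | 0 | 77% | 82% |
| 0.9 | 0 | 77% | 79% |
| 0.5 | 0.6 | 73% | 86% |
| 0.7 | 0.6 | 73% | 82% |
| 0.9 | 0.6 | 72% | 77% |

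Mann-Whitney size at 0.6 SD is 3.4 to 4.1%, in line with the approximation. Rank ANCOVA size is 4.3 to 5.6%. Stratification alone (van Elteren) gains about 0 to 4 points up to 0.6 SD.

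**Skewed scores (lognormal, log-SD 0.7, 2,000 runs, r 0.5 to 0.95).** Mann-Whitney on absolute change has 59 to 67% power and rank ANCOVA of absolute change 70 to 81%. Mann-Whitney on percent change, already planned for F-VASI and T-VASI, has 73 to 77%. Rank ANCOVA of absolute change clearly beats that last test only at r = 0.5. VES and VitiQoL have no percent-change test.

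**Do the mixed models fill the gap?** They have no stratum term and do not reach Weeks 36 and 48. Day 0 is an outcome whose mean is free in each arm, so with complete data the contrast of change from baseline is the difference in mean change. That is not a comparison adjusted for baseline.

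**The case against.** The strongest reply is that these tests are valid, simple and only supportive. They control type 1 error, need no model for the covariate with 38 against 19 participants, and no decision rule or sample size depends on them. All of that stands and is why the severity is low.

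Other parts also stand. A reader might infer that the tests ignore baseline. They do not: change and percent change are both built from it, and what is missing is adjustment for it as a covariate. A reader might infer that adjustment costs nothing. Rank ANCOVA assumes a roughly linear relation between ranks, and parametric ANCOVA did slightly worse than Mann-Whitney on change in the skewed case at r = 0.95 (63 to 64% against 64 to 67%). A reader might also infer that the planned p-values are badly too large. That needs active and stable patients to differ by a full SD of change or more; at 1 SD the size falls to about 2.5%. The documents give no effect of that size.

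The Week 36 and 48 comparisons are a weak ground for the change. Participants below a 25% T-VASI improvement at Week 24 then receive phototherapy (Section 7.3), so added precision there would not isolate the drug effect. The gain matters mainly at Weeks 12 and 24.

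What the reply does not answer is that a rank-based adjusted test keeps most of the robustness and uses data already collected.

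**Conclusion.** The point holds as an efficiency improvement to a valid analysis. With normal data and no stratum effect, rank ANCOVA gains about 9 points of power at r = 0.5, 5 at r = 0.7 and 2 at r = 0.9. With a stratum effect of 0.6 SD of change it gains about 13, 9 and 5 points, and the Mann-Whitney size is then 3.4 to 4.1% instead of 5%. Most of the gain comes from the baseline covariate when r is moderate; stratification alone adds little unless activity is strongly prognostic. For skewed F-VASI and T-VASI, the planned percent-change test leaves little to recover except at low correlation.

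These figures rest on the assumed correlations, stratum effects and distributions, since the documents supply none. They do not show that any planned test is invalid or that the primary conclusion is at risk. Severity is low.

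**What to change.** In Section 13.4.4, item 3, replace the Mann-Whitney tests by a rank ANCOVA of change (and of percent change for F-VASI and T-VASI) with treatment, baseline score and active/stable stratum. At the least, use the stratified Wilcoxon (van Elteren) test. Keep the unadjusted Mann-Whitney test as a sensitivity analysis, which also covers the case where the ranks are not linearly related.

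In item 5, add the stratum to the mixed models together with its interaction with time point. A main effect alone shifts all visits equally and would not alter the contrasts of change from baseline.

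The cost is a few lines of analysis-plan text and standard code. Baseline scores and stratum are already collected, and sample size and visits do not change. The change should be fixed before unblinding, so that the choice of test cannot depend on the results.

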# 13.4.2 Primary Analysis of Primary Endpoint

The primary endpoint is the proportion of participants achieving an F-VASI35 response at Week 24.

The primary analysis of the primary endpoint will be performed on the mITT sample and is designed to test the following hypotheses:

- Null hypothesis: The proportion achieving an F-VASI35 at Week 24 does not differ between the AMG 714 and placebo groups
- Alternate hypothesis: The proportion achieving an F-VASI35 at Week 24 differs between the AMG 714 and placebo groups.

The proportion of F-VASI35 responders will be estimated for each treatment group. Groups will be compared using two-sided Fisher's Exact test evaluated using a Type 1 error rate of  $\alpha$ =0.05.

**Missing Data.** For a participant who is missing the baseline F-VASI, the screening F-VASI will be used. Participants for whom the Week 24 F-VASI cannot be evaluated will be deemed non-responders.

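### Durability item 1b states a one-sided test of worsening but gives VNS Bowker's test, which has no direction; the between-arm VNS test in item 4a should also be named and use the ordering

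*Combined protocol and SAP*

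**What the plan says.** Appendix 5 defines VNS as five ordered answers, from 1 (more noticeable than before treatment) to 5 (no longer noticeable), and counts 4 or 5 as success. Section 3.3.1 lists VNS as item 4e of the secondary efficacy endpoints. No endpoint or analysis uses the success rule.

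Section 13.4.4 treats VNS in these places:

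- **Between arms (item 4a).** The endpoint is called ordinal, and "Treatment groups will be compared at each indicated secondary analysis time point using an extension of the Fisher's Exact test". Item 3 gives the changes in F-VASI, T-VASI, VES and VitiQoL two-sided Mann-Whitney tests.
- **Durability (item 1).** Among Week 24 T-VASI25 responders, no change is tested within each arm "against the 1-sided alternative of worsening from Week 24 to Week 48". Item 1a uses Wilcoxon tests for the other scales. Item 1b says of VNS that "shifts in distributions from Week 24 to Week 48 will be evaluated for each treatment arm using Bowker's exact test of symmetry".

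The same section labels all secondary inference supportive and unadjusted. Power is stated only for the primary F-VASI35 endpoint: "a study of 57 individuals randomized 2:1 to AMG 714 and placebo, respectively, will provide 88% power using a 2-sided Fisher's Exact test at" the 0.05 level.

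**The concern.** A one-sided alternative needs a statistic that moves one way for worsening and the other way for improvement. Bowker's statistic squares the imbalance in each pair of categories, so the sign is lost. With a single pair of categories (McNemar's case) a one-sided version exists. Across several pairs it does not.

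Durability is a stated secondary objective (Section 2.3). For VNS, the planned p-value could be small because participants kept improving, or large although every participant who moved got worse.

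Item 4a raises a lesser question. If the unnamed extension is the usual r x c (Fisher-Freeman-Halton) test, its p-value is the same however the five categories are arranged. It then makes no use of the ordering that the plan itself recognises.

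**Working it through.** **1. The plan's own power figure.** Inputs from Section 13.7: 57 participants at 2:1, so 38 v 19; rates 45% v 5%; two-sided 0.05. The continuity-corrected arcsine approximation to Fisher's test is Φ(2h/√(1/n₁+1/n₂) − 1.96), with h = asin√(p₁ − 1/(2n₁)) − asin√(p₂ + 1/(2n₂)). Here h = asin√0.4368 − asin√0.0763 ≈ 0.442 and √(1/38 + 1/19) ≈ 0.281, giving 88.2% against the stated 88%. The other two stated figures also reproduce (80.9% for 81%, 80.3% for 80%). They concern F-VASI35, and nothing below changes them. No VNS power is stated.

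**2. Bowker's test and direction (item 1b).** The statistic is Σ (n_ij − n_ji)² / (n_ij + n_ji) over category pairs. Swapping worsening and improvement swaps n_ij and n_ji and leaves it unchanged. Under symmetry, each pair with m movers follows a Binomial(m, ½). If all k movers go the same way across c pairs, the statistic is at its maximum and the exact p is 2^(c−k). If every move is one category, the one-sided signed-rank and sign tests both give 2^(−k) for worsening and 1.0 for improvement.

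| Movers, all one category in the same direction | c | k | Exact Bowker, all worse | Exact Bowker, all better | One-sided, all worse | One-sided, all better |
|---|---|---|---|---|---|---|
| three 4→3, two 5→4, one 3→2 (or the reverse) | 3 | 6 | 2^(−3) = 0.125 | 0.125 | 2^(−6) = 0.016 | 1.0 |
| 5→4, 4→3, 3→2, 2→1, one each (or the reverse) | 4 | 4 | 2^0 = 1.0 | 1.0 | 2^(−4) = 0.0625 | 1.0 |
| nine movers over three pairs, among 20 | 3 | 9 | 2^(−6) = 0.0156 | 0.0156 | 2^(−9) = 0.002 | 1.0 |

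**3. Power in the durability subset.** The documents give neither its size nor its VNS distribution. Assumptions: Week 24 scores of 2/3/4/5 in 20/35/30/15%; 40% worsen by one category and up to 5% improve; 3,000 simulated data sets. Exact Bowker v one-sided sign test: 1% v 28% with 10 responders in an arm, 24% v 64% with 17, 58% v 84% with 25. Part of this gap arises because the sign test spends all of its 5% on worsening, which is what the stated hypothesis asks for.

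**4. Between arms (item 4a), 38 v 19, two-sided 0.05.** All distributions are assumed, given as percentages over scores 1 to 5.

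| Assumed scenario (placebo v AMG 714) | Unordered Fisher | Rank-sum |
|---|---|---|
| Placebo 25/50/15/8/2, odds ratio 2 / 3 / 4 / 6 | 13 / 28 / 47 / 75% | 26 / 53 / 74 / 92% |
| Placebo 20/40/25/10/5, odds ratio 2 / 3 / 4 / 6 | 14 / 34 / 51 / 79% | 26 / 57 / 76 / 94% |
| 15/55/22/6/2 v 8/35/30/20/7 | 30% | 54% |
| 10/60/25/4/1 v 5/35/30/22/8 | 45% | 68% |
| 15/50/25/8/2 v 8/30/27/25/10 | 34% | 58% |
| Success 5% v 45%: 10/60/25/4/1 v 5/25/25/33/12 | 84% | 93% |
| Success 5% v 45%: 15/55/25/4/1 v 10/25/20/33/12 | 79% | 81% |
| Success 5% v 45%: 15/55/25/4/1 v 8/30/17/33/12 | 75% | 81% |
| Mixture: 10/60/25/4/1 v 10/38/7/33/12 | 83% | 51% |

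The odds-ratio rows assume proportional odds, with 1,500 simulated trials each, so the simulation error is about √(0.5 × 0.5/1500) = 1.3 points. Their gains run from 12 to 27 points. At 5% v 45% success the gains shown are 9, 2 and 6 points, and a repeat at two such distributions gave about 4 to 7. In the mixture row the ranking reverses. Type 1 error was about 4 to 5% for both tests.

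Fisher's test on success (4 or 5) alone does not replace an ordered test: at odds ratio 3 its power was 22% and 27% for the two placebo distributions.

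**The case against.** The case against is strong for item 4a. The test is valid and two-sided, it holds its level, and it matches the section's general alternative that the groups differ. Direction can be read from the reported distributions. The unnamed extension could be an ordered exact test, and the unordered version does better when some participants respond strongly and the rest do not. All of this stands: item 4a is a matter of efficiency and clear naming, not an error.

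A reader might also infer three stronger things that the documents do not support.

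- **That VNS is the main patient-reported measure of repigmentation.** Section 3.3.1 lists it after VitiQoL without ranking, Appendix 5 asks about noticeability, and repigmentation is carried by F-VASI and T-VASI, which have ordered tests.
- **That a real benefit is likely to be missed.** No VNS distribution is given. At an effect like the design assumption for F-VASI35, the unordered test has 75 to 84% power in the assumed distributions.
- **That the one-sided durability test cannot be done at all.** The Wilcoxon tests in item 1a can be one-sided for the other four scales. Only VNS is affected.

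The supportive status of VNS limits the consequence. It does not remove the mismatch in item 1b, which does not depend on any assumed distribution.

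**Conclusion.** Item 1b is wrong as written. The hypothesis is directional, and the test assigned to VNS returns the same p-value for uniform worsening and uniform improvement (0.125 both ways in the six-person example, against 0.016 and 1.0 for a one-sided signed-rank test). This is a property of the test and needs no assumption. The power figures for the durability subset do rest on assumed sizes and movements.

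Item 4a is a cheap improvement. An ordered test gains roughly 4 to 27 points under assumed shifts towards better scores, least when success is as far apart as 5% v 45%. It can lose about 32 points (83% − 51%) under a responder/non-responder mixture. No decision in the plan depends on a VNS p-value, and the primary comparison and its stated power are untouched.

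**What to change.** **Item 1b (needed).** Replace Bowker's test with a one-sided exact Wilcoxon signed-rank test, within each arm, of a decrease in VNS from Week 24 to Week 48. A one-sided sign test would also serve. State how zero changes and ties are handled. Item 1a does not say exact, so the word has to be written in. The Week 24 by Week 48 table can stay as description.

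**Item 4a (recommended).** Name the test, and make it the two-sided Mann-Whitney test that item 3 uses for the other scales. Report the proportion with VNS 4 or 5 by arm with a confidence interval at each visit, as an estimate. Count missing scores as failures, as Section 13.4.4 already does for the other response indices. Add this proportion to Section 3.3.1.

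**Cost.** No new data are needed: Appendix 1 already schedules VNS at Weeks 12, 24, 36 and 48. The affected text is in the protocol, so this is an amendment needing IRB approval before use (Section 17.1), and it should be settled before treatment codes are released for analysis. The price of the item 4a change is the loss of power against a mixture-type effect. The success proportion by arm would help to show such an effect.

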#### 3.3 SECONDARY ENDPOINTS

## 3.3.1 Secondary Efficacy Endpoints

- 1. Proportion of participants with F-VASI35 at Weeks 12, 36, and 48.
- 2. Proportion of participants with F-VASI25, F-VASI50, F-VASI75, and F-VASI90 at Weeks 12, 24, 36, and 48.
- 3. Proportion of participants with T-VASI25, T-VASI35, T-VASI50, T-VASI75, and T-VASI90 at Weeks 12, 24, 36 and 48.
- 4. Change in each of the following at Weeks 12, 24, 36, and 48 compared to Week 0:
  - a. F-VASI
  - b. T-VASI
  - c. Vitiligo Extent Score (VES)36
  - d. Vitiligo Quality of Life instrument (VitiQoL)
  - e. Vitiligo Noticeability Scale (VNS)38
  - f. Static Investigator Global Assessment (sIGA)
- 5. Percent change in each of the following at Weeks 12, 24, 36, and 48 compared to Week 0:
  - a. F-VASI
  - b. T-VASI

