    - i. Shifts in distributions from baseline to Week 48 will be evaluated for each treatment arm using Bowker's exact test of symmetry.

Treatment group differences for the incidence of AEs and the incidence of grade 3 or higher infectious AEs occurring over the first 24 weeks will be compared using a Fisher's exact test.

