# APPENDIX 4. VITIQOL

Vitiligo-specific Health-related Quality-of-life Instrument (VitiQoL) is a validated instrument that asks participants to rate various aspects of their vitiligo during the past month. Assessment will be conducted at the baseline visit, as well as visits during and after treatment per Appendix 1. The response to each question will be scored on a 0 (not at all) to 6 (all of the time) scale.

Du	ring the past month,	Not at all					All	of e time
		4			•			4
1.	Have you been bothered by the appearance of your skin condition?		ο,	□₂		□₄	□,	۵,
2.	Have you felt frustrated about your skin condition?	□₀	$\Box$ ,			□₄	□₅	□₊
3.	Has your skin condition made it hard to show affection?	$\Box$	$\Box$	Π,	□,	$\Box_4$	□,	$\Box_{\iota}$
4.	Has your skin condition affected your daily activities?	□.			D 3	□₄	□₅	□,
5.	When you were talking to someone, have you worried about what they may be thinking of you?	.	- 1	□₂	D 3	□ ₄		□,
6.	Have you been afraid that people will find fault with you?	□∘			D 3	□₄	□₅	□,
7.	Have you felt embarrassed or self-conscious because of your skin?	.	-	□₂	□,	ا	- ;	п ,
8.	Has your skin condition influenced the clothes you wear?	$\Box$			Π,	۵	□s	□₊
9.	Has your skin condition affected your social or leisure activities?	□.	$\Box$ ,		□,	□₄	□,	□,
10.	Has your skin condition affected your emotional well-being?	□.	$\Box$ ,		□,		□,	□,
11.	Has your skin condition affected your overall physical health?	□₀	$\square_1$		□,	□₄	□,	□,
12.	Has your skin condition affected your grooming practices (i.e. hairstyle, use of cosmetics)?	.		□ ₂	D 3	۵,	- .	۵,
13.	Has your skin condition affected your sun protection efforts during recreation (i.e. limiting exposure time during peak sun hours, seeking shade, wearing hat, long sleeves or pants)?	.	- ,	D 2	σ,	□₄	ο,	□,
14.	Has your skin condition affected your chances for making new friends?	.	ο,	D 2	□,	□₄	□,	□ .
15.	Have you worried about progression or spread of disease to new areas of the body?	□.	ο,	۵	ο,	□₄	۵	□,
	se check how severe you currently feel your condition is:	No ski involve					severe	Most case
16.	Severity of skin condition.		П.	П.	П	Π.	Π.	П.

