# **APPENDIX 5. VNS**

Vitiligo Noticeability Scale (VNS) is a validated patient-reported outcome measure of vitiligo treatment. Participants will be presented with one pre-treatment photograph of their face at different visits (see Schedule of Events, Appendix 1) and asked to answer the question below. The same pre-treatment photograph must be used at each visit.

Question	Response option (Score)	Success criteria				
Compared with before treatment, how noticeable is	More noticeable (1)	Score of 4 or 5				
the vitiligo now?	As noticeable (2)					
	Slightly less noticeable (3)					
	A lot less noticeable (4)					
	No longer noticeable (5)					

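### Ten planned tests of VNS shift from baseline have no baseline score: VNS is not collected before treatment, and each score is already a rating of change

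*Combined protocol and SAP*

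**What the plan says.** Section 3.3.1 item 4 defines the endpoint as "Change in each of the following at Weeks 12, 24, 36, and 48 compared to Week 0"; VNS is entry e in that list. Section 8.2.2 sets baseline at Week 0.

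Section 13.4.4 plans three sets of Bowker tests on VNS:

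- **Item 4b, all mITT participants:** "Shifts in distributions from baseline to each time point will be evaluated for each treatment arm using Bowker's exact test of symmetry".
- **Item 2c(i), participants who miss T-VASI25 at Week 24 and receive nbUVB:** "Shifts in distributions from baseline to Week 48 will be evaluated for each treatment arm using Bowker's exact test of symmetry".
- **Durability item 1b, T-VASI25 responders:** Week 24 against Week 48 within each arm. The lead-in to item 1 says the null of no change "will be evaluated by treatment arm against the 1-sided alternative of worsening from Week 24 to Week 48".

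Appendix 5 describes the instrument. The question opens "Compared with before treatment, how noticeable is", and the participant answers for the current visit on a scale from 1 (worse) through 2 (no change) to 5 (no longer visible). On the reference picture it says: "The same pre-treatment photograph must be used at each visit".

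On missing secondary data, Section 13.4.4 counts unavailable response indices as failures and then says: "Otherwise, data will not be imputed for analyses of secondary endpoints".

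**The concern.** A test of symmetry compares two scores from the same person. Items 4b and 2c(i) take the first of these at baseline, but the plan collects no VNS then and gives no rule for deriving one. The analysis text treats VNS as a status scale measured before and after treatment. Appendix 5 makes it a transition scale, on which every score is already a comparison with the pre-treatment state.

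VNS is one of only two patient-reported efficacy scales in Section 8.3.5. If the text stands, the within-arm VNS analyses cannot be produced, and a substitute would have to be chosen later, possibly with the data in view. The Week 24 to Week 48 test has a different problem: its stated alternative has a direction and the test does not.

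**Working it through.** The documents give no figure for the VNS analyses, so there is none to reproduce. The check is a reading of the schedule, a count of tests, and two small exact calculations.

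**1. When VNS is collected (Appendix 1)**

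| Scale | Visits marked |
|---|---|
| VNS | Weeks 6, 12, 24, 36, 48, withdrawal |
| VES | Weeks 0, 6, 12, 24, 36, 48, withdrawal |
| VitiQoL | Weeks 0, 6, 12, 24, 36, 48, withdrawal |
| sIGA | Weeks 0, 12, 24, 36, 48, withdrawal |

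The other three rows keep their Week 0 mark, so the VNS blank is not a column lost in the table. Appendix 4 agrees with its row; for VitiQoL it says "Assessment will be conducted at the baseline visit, as well as visits during and after treatment per Appendix 1". Appendix 5 has no such statement. Adding a Week 0 VNS would not help, because a comparison with before treatment has no meaning before treatment starts.

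**2. Number of tests affected**

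Section 3.3.1 gives four VNS time points (Weeks 12, 24, 36, 48), and there are two arms.

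- Item 4b: 4 x 2 = 8, none with a baseline score.
- Item 2c(i): 1 x 2 = 2, none with a baseline score.
- Durability item 1b: 1 x 2 = 2, both scores collected.

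So 8 + 2 = 10 of 12 have no input. Week 6 is collected but is not a listed secondary time point, so it is not counted.

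**3. Would setting every baseline to 2 rescue the tests?**

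The plan does not state this; it is the obvious workaround. With a constant baseline, all data fall in one row of the 5 x 5 table. Each off-diagonal pair then has one empty cell by construction. Under symmetry, each pair with k observations is Binomial(k, 1/2), and having all k on one side is the most extreme result, so

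p = product over occupied cells of 2 x (1/2)^k.

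Hypothetical example: 4 participants better (score 3) and 4 worse (score 1).

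- Exact Bowker: (2 x 0.5^4)^2 = 0.125^2 = 0.0156.
- Two-sided sign test against 2, with 4 up and 4 down: p = 1.0.

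The workaround reports a clear shift when equal numbers improved and worsened. It responds to any movement away from 2, in either direction.

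**4. Direction of the Week 24 to Week 48 test**

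Hypothetical example: six participants change, three between scores 5 and 4 and three between 4 and 3.

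- All six worse: exact Bowker p = (2 x 0.5^3)^2 = 0.25^2 = 0.0625.
- All six better: the same tables transposed, p = 0.0625.
- One-sided sign test for worsening, six of six worse: 0.5^6 = 0.0156.

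Bowker's test gives the same answer for uniform loss and uniform gain, so it does not test the stated alternative.

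**The case against.** The case against concedes that no baseline VNS is collected and argues about scope.

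- **The count.** Ten tests come from one phrase applied to one instrument, and item 2c(i) is the Week 48 test of item 4b in a subset. That is fair: this is one defect, and ten measures its reach.
- **Endpoint 4e.** Because the score is a rating against the pre-treatment state, it can be read as the change from Week 0, and item 4a can compare it between arms. This largely stands. The endpoint needs a clarifying definition and remains usable.
- **The imputation sentence.** It is a missing-data rule and may not have been meant to exclude a reference value implied by the scale. This stands too. The sentence is supporting evidence only; what matters is that no rule supplies a baseline score.
- **The constant-baseline example.** It tests something the plan does not propose. True, but it shows why the easiest repair would mislead. A one-sample test against 2 uses the same reference value and does respect direction.
- **Week 24 to Week 48.** Item 1b does not itself call the Bowker test one-sided, and direction can be read from the shift table. But it sits under a lead-in that sets a one-sided alternative, so the mismatch remains.
- **Consequence.** These are supportive, within-arm analyses without multiplicity control. Agreed, and this sets the severity.

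**Conclusion.** The concern holds, at minor severity. As written, 10 of the 12 planned VNS Bowker tests cannot be run, because no baseline score is collected and the scale has none by design. This rests on the Appendix 1 schedule, the Appendix 5 question and the Section 8.2.2 definition of baseline, and needs no outside assumption. The remaining 2 tests can be run but do not match the one-sided alternative set for them.

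The p-values above use hypothetical counts; they show how the tests behave and predict nothing about the trial. The primary endpoint, its power, the sample size and the between-arm VNS comparison in item 4a are not affected.

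**What to change.** Amend the wording before unblinding:

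1. **Section 3.3.1 item 4e (and the synopsis):** define the endpoint as the VNS score at Weeks 12, 24, 36 and 48, plus the proportion meeting the Appendix 5 success criterion (score 4 or 5). State that the score is itself the rating of change from the pre-treatment state.
2. **Section 13.4.4 items 4b and 2c(i):** delete the baseline-to-visit Bowker tests, or replace each with a one-sample sign or signed-rank test against score 2. The sign test asks less of the scale, which has one category below 2 and three above.
3. **Durability item 1b:** replace Bowker's test with a one-sided paired sign or signed-rank test for worsening from Week 24 to Week 48, with the shift table shown beside it.

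The cost is protocol and SAP text only. No new visits, data or participants are needed.
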